### **3.5.3.8 Exercise adherence**

Below analysis applies to both population I and population II.

During the study, patients will be instructed to complete an Exercise Adherence e-diary. The diary will capture physical activity per defined categories in the diary. [REDACTED]

[REDACTED]

[REDACTED]

For each exercise category, summary statistics for the total time spent will be provided by treatment group (for population I, and treatment assigned in the core study for population II) and visit.

### **3.5.3.9 Other assessments**

#### **400 Meter Walk Test**

400 meter walk test was removed upon protocol amendment 1. If any data captured prior to protocol amendment 1 are available in the database, those will be listed only, by treatment arm at the final analysis.

### 3.5.4 Supportive analysis

The same analysis defined above for the Gait speed, 6MWD, [REDACTED], and total LBM will also be performed [REDACTED]:

- [REDACTED]
- [REDACTED]

## 3.6 Statistical methods for safety and tolerability data

Analyses in this section will be based on SAF.

For Population I, all summaries will be presented by treatment group in the extension study and overall. For Population II, all summaries will be presented by treatment assigned in the Core study and overall. [REDACTED]

Relevant raw and derived data as described in this section will also be presented in by-patient data listings. All by-patient data listings will be sorted by treatment group, [REDACTED] center and patient if not indicated otherwise.

Descriptive statistics (mean, median, standard deviation, minimum and maximum) for safety variables will be presented for the SAF analysis set.

Where relevant, “overall” refers to the addition of a “Total” treatment column within the planned presentation of the data.

### 3.6.1.1 Variables

Adverse events, vital signs (blood pressure, pulse rate, body temperature), ECG intervals, laboratory measurements, echocardiography, [REDACTED], nutrition status and protein intake, as well as subject demographics, baseline characteristics, and treatment information.

### 3.6.1.2 Descriptive analyses

#### Vital signs

Vital signs include height (cm), weight (kg), BMI (kg/m^2), temperature (°C), pulse (beats/min), mean systolic blood pressure (SBP) (mmHg) and mean diastolic blood pressure (DBP) (mmHg). Height will be measured only once at Screening, hence BMI will be calculated for each visit using the Screening value of height and with the actual body weight value measured at the scheduled visit. Mean sitting SPB/DBP will be calculated from the three assessments taken per visit and will be used for tabulation (as recorded in the Vital Signs eCRF).

Summary statistics (including mean, SD, median, minimum and maximum) will be provided by treatment and visit/time, for each population separately.

For population I, notable vital signs values will be considered “newly occurring” if they had not been present at Week 25 but present during the treatment epoch. If assessments cannot be made at Week 25 due to missing value(s), post-Week 25 values meeting the notable criterion will be considered as newly occurring. Similar definition applies for population II, post-treatment follow-up epoch. Notable vital signs are considered to be the following:

- Systolic blood pressure:
  - >150mmHG or increase from Week 25 of  $\geq 20$  mmHg
  - <90mmHG or decrease from Week 25 of  $\geq 20$  mmHg
- Diastolic blood pressure:
  - >90mmHG or increase from Week 25 of  $\geq 15$  mmHg
  - <50mmHG or decrease from Week 25 of  $\geq 15$  mmHg
- Pulse rate:
  - >100bpm or increase from Week 25 of  $\geq 15$  bpm
  - <60bpm or decrease from Week 25 of  $\geq 15$  bpm

Summaries of newly occurring notable values will be summarized by population and by epoch.

All vital signs data will be listed by population, treatment, subject, and visit/time and if ranges are available abnormalities (and relevant orthostatic changes) will be flagged.

### **ECG evaluations**

Summary statistics (including mean, SD, median, minimum and maximum) will be presented for ECG variables by visit and treatment group, for each population separately.

The following quantitative variables will be summarized: ventricular rate, RR interval, PR interval, QRS duration, QT interval, and corrected QT interval (QTc). Both Bazett (QTcB) and Fridericia (QTcF) corrections will be presented for QTc.

QTc will also be summarized by computing the number and percentage of subjects with:

- QTc > 500 msec
- QTc > 480 msec
- QTc > 450 msec
- PR > 250 msec
- QTc change from Week 25 > 30 msec
- QTc change from Week 25 > 60 msec

A listing of all newly occurring or worsening abnormalities by epoch will be provided for both populations, as well as a by-subject listing of all quantitative ECG parameters.

### **Clinical laboratory evaluations**

All laboratory data will be listed by Population, treatment, subject, and visit/time and if normal ranges are available abnormalities will be flagged. A separate listing is provided presenting all parameters in a subject with any abnormal values. Summary statistics (including mean, SD, median, minimum and maximum) will be provided by treatment and visit/time for Hematology, Clinical chemistry and Coagulation testing, for each population separately. For urinalysis, frequency tables will be presented.

Summaries of newly occurring notable values will be similar to those of vital signs.

[figure not shown]
Notable values are values which are considered as:

- Low: Value below the lower limit of the normal range (LLN).
- High: Value above the upper limit of the normal range (ULN).

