Descriptive summary statistics for each study visit will be presented. These descriptive summaries will be presented by test group, laboratory test and treatment group.

Subjects with abnormal laboratory values will be listed and selected parameters will be flagged during study conduct according to pre-defined clinically relevant values.

Newly occurring or worsening liver enzyme abnormalities will be summarized.

ECG

Summary statistics for Populations I and II separately will be presented for ECG variables by visit and treatment group.

The following quantitative variables will be summarized: ventricular rate, RR interval, PR interval, QRS duration, QT interval, and corrected QT interval (QTcF).

QTcF will be summarized by computing the number and percentage of subjects with:

- QTc > 500 msec
- QTc > 480 msec
- QTc > 450 msec
- PR > 250 msec

A listing of all newly occurring or worsening abnormalities will be provided, as well as a by-subject listing of all quantitative ECG parameters.

[figure not shown]
Echocardiography

For Population I summary statistics will be presented by visit and treatment group for the following measurements:

- Left ventricular wall (anterior and posterior) and septal thickness
- Left ventricular mass and mass index
- End-diastolic volume
- End-systolic volume
- Left ventricular ejection fraction
- Left ventricular diastolic and systolic diameter

- Left atrial size and volume
- Right ventricular wall thickness and function
- Interrogation of all valves for function, stenosis, regurgitation and morphology

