LIVER LABORATORY TRIGGERS	
• $3 \times \text{ULN} < \text{ALT} / \text{AST} \leq 5 \times \text{ULN}$• $1.5 \times \text{ULN} < \text{TBL} \leq 2 \times \text{ULN}$
LIVER EVENTS	
• $\text{ALT or AST} > 5 \times \text{ULN}$• $\text{ALP} > 2 \times \text{ULN}$ (in the absence of known bone pathology)• $\text{TBL} > 2 \times \text{ULN}$ (in the absence of known Gilbert syndrome)• $\text{ALT or AST} > 3 \times \text{ULN}$ and $\text{INR} > 1.5$• Potential Hy's Law cases (defined as $\text{ALT or AST} > 3 \times \text{ULN}$ and $\text{TBL} > 2 \times \text{ULN}$ [mainly conjugated fraction] without notable increase in ALP to $> 2 \times \text{ULN}$)• Any clinical event of jaundice (or equivalent term)• $\text{ALT or AST} > 3 \times \text{ULN}$ accompanied by (general) malaise, fatigue, abdominal pain, nausea, or vomiting, or rash with eosinophilia• Any adverse event potentially indicative of a liver toxicity *

Table 13-2 Follow Up Requirements for Liver Events and Laboratory Triggers

Criteria	Actions required	Follow-up monitoring
Potential Hy's Law case ^a	
 Discontinue the study drug immediately Hospitalize, if clinically appropriate Establish causality Complete liver CRF 	ALT, AST, TBL, Alb, PT/INR, ALP and γ GT until resolution ^c (frequency at investigator discretion)
ALT or AST		
> 8 × ULN	
 Discontinue the study drug immediately Hospitalize if clinically appropriate Establish causality Complete liver CRF 	ALT, AST, TBL, Alb, PT/INR, ALP and γ GT until resolution ^c (frequency at investigator discretion)
> 3 × ULN and INR > 1.5	
 Discontinue the study drug immediately Hospitalize, if clinically appropriate Establish causality Complete liver CRF 	ALT, AST, TBL, Alb, PT/INR, ALP and γ GT until resolution ^c (frequency at investigator discretion)
> 5 to ≤ 8 × ULN	
 Repeat LFT within 48 hours If elevation persists, continue follow-up monitoring If elevation persists for more than 2 weeks, discontinue the study drug Establish causality Complete liver CRF 	ALT, AST, TBL, Alb, PT/INR, ALP and γ GT until resolution ^c (frequency at investigator discretion)

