^b(General) malaise, fatigue, abdominal pain, nausea, or vomiting, or rash with eosinophilia

^cResolution is defined as an outcome of one of the following: (1) return to baseline values, (2) stable values at three subsequent monitoring visits at least 2 weeks apart, (3) remain at elevated level after a maximum of 6 months, (4) liver transplantation, and (5) death.

14 Appendix 2: Sample Log

Sample Log (all matrices): Time schedule for collection of blood for safety, [REDACTED] and pharmacodynamic (PD) assessments as per Table 6-1 and 6-2 as appropriate.

Sample volumes are the maximum size at any given visit.

For patients newly enrolled following protocol amendment#1

Study Epoch	Visit #	Day	Safety ¹
			size (ml)
SCR	1	1	
Post Treatment Follow-up	1	1	30*
	2	85	30
	3	169	30

¹ Includes when applicable: clinical chemistry (incl. vitamin D), hematology,
* Sample collected at EOT visit of the core study E2202

For patients enrolled prior to protocol amendment #1. All samples are to be collected pre-dose.

Study Epoch	Visit #	Day	Safety ¹	
			size (ml)	
SCR	1	1		
Treatment	1	1		
	2	29	30	
	3	57		
	4	85	30	
	5	113		
	6	141		
	7	169	30	
Post Treatment Follow-up	8	197	30	

¹ Includes when applicable: clinical chemistry (incl. vitamin D), hematology,

[REDACTED]

[REDACTED]

15 Appendix 3: Clinically notable laboratory values:

The following criteria will be used as guidance for notable abnormalities of key laboratory tests and vital signs.

Clinically notable values will be forwarded to Novartis at the same time that they are sent to the investigators. Any action based on these laboratory values should be discussed with Novartis personnel.

Table 15-1 Clinically notable lab values

Laboratory Variable	Notable Criteria
Hemoglobin	<8.0 g/dL
Glycated hemoglobin (HbA1c)	≥7.5%
Average blood glucose	≥9.0 mmol/L
Platelet count	<75000 mm ³
Estimated GFR	<30 mL/min
Total bilirubin concentration	>1.5 x ULN
Total serum bilirubin	>1.6 mg/dL (27µmol/L)
AST	>3xULN
ALT	>3xULN

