### **3.8 Interim analyses**

An interim analysis will be triggered by the analysis of the core study Part A. Data from primary and key secondary efficacy parameters will be summarized. The interim analysis will provide a preliminary evaluation of endpoints over approximately 12 months; and together with core study Part A data will support next step decision making. Analyses based on PP set will not be included for IA.

The interim analysis will cover following analyses:

- Patient disposition
- Analysis sets
- Demographics and patient characteristics at Week 25 (nutritional status, protein intake, 6MWT, SPPB total score, Gait Speed, [REDACTED], and ASMI)
- Treatments (Study drug for population I, prior and concomitant medication for both populations)

- Primary analysis: SPPB at Week 49, summaries of population I and II separately
- Secondary analyses: 6MWT, Gait speed, LBM and ASMI, summaries for population I and II separately

- █ [REDACTED]
- Safety analyses:
    - Nutrition status/protein intake
    - Population I: TEAE, ECG, Vital sign, and notable Lab
    - Population II: notable Lab.
  - Supportive analysis:
    - Proportion of sarcopenic patients at Week 25 vs Week 49.

█ [REDACTED] Such analysis will be detailed in a separate document when it becomes necessary and/or be generated for the final analysis.

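### The SAP's notable-laboratory table can miss patients who cross a protocol Table 15-1 threshold after Week 25, and its liver table has no standalone total bilirubin >2 x ULN row

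*SAP*

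**What the plan says.** **General laboratory values.** SAP 3.6.1.2, Clinical laboratory evaluations, has two cuts for every analyte: "Low: Value below the lower limit of the normal range (LLN") and "High: Value above the upper limit of the normal range (ULN"). It then states: "Summaries of newly occurring notable values will be similar to those of vital signs". The vital-signs text in the same section counts a notable value as newly occurring only if it was absent at Week 25. If the Week 25 value is missing, a later notable value counts.

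**Protocol criteria.** Appendix 3 introduces Table 15-1 with "The following criteria will be used as guidance for notable abnormalities of key laboratory tests and vital signs", and adds "Clinically notable values will be forwarded to Novartis at the same time that they are sent to the investigators". Section 9.5.2 asks for a listing of subjects with abnormal values and says that "selected parameters will be flagged during study conduct according to pre-defined clinically relevant values".

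**Liver values.** The SAP liver section has standalone total bilirubin (TBL) rows at >1.5 and >3 x ULN. It uses TBL >2 x ULN only in combination with ALT/AST >5 x ULN or ALP >5 x ULN. It also lists Hy's law, without a definition. Protocol Table 13-1 makes TBL >2 x ULN a liver event ("in the absence of known Gilbert syndrome"), and Table 13-2 gives isolated TBL >2 x ULN its own follow-up actions.

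**Interim.** Under safety analyses, SAP 3.8 names nutrition status and protein intake and, for the off-drug cohort, "Population II: notable Lab".

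**The concern.** The two documents use the word notable for different things. In the protocol it marks a short list of pronounced abnormalities; in the SAP's general laboratory table it marks any departure from the reference range. A wide definition combined with a rule that removes patients already notable at Week 25 does more than dilute the table. It can leave out a patient who worsens from a mild to a pronounced abnormality during the extension, which is a change that a post-treatment safety summary is meant to show.

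The liver table has a related gap. The level at which the protocol turns a bilirubin laboratory trigger into a liver event is not a standalone row, so the count of such events cannot be read from the table.

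**Working it through.** The plan states no figure to reproduce here. The check compares thresholds line by line.

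**Step 1: Table 15-1 against the SAP's count rows.**

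| Protocol Table 15-1 criterion | Same cut in a SAP count table? |
|---|---|
| Hemoglobin <8.0 g/dL | No |
| HbA1c >=7.5% | No |
| Average blood glucose >=9.0 mmol/L | No |
| Platelets <75000 | No |
| Estimated GFR <30 mL/min | No |
| Total bilirubin >1.5 x ULN | Yes |
| Total serum bilirubin >1.6 mg/dL | No |
| AST >3 x ULN | Yes, pooled with ALT |
| ALT >3 x ULN | Yes, pooled with AST |

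Three of nine are covered and 9 - 3 = 6 are not. Of those six, five are non-liver. The sixth is bilirubin in absolute units, for which the >1.5 x ULN row is a near relative.

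**Step 2: the newly-occurring rule applied to a worsening patient.** Take hemoglobin, and assume that the laboratory's lower limit is above 8.0 g/dL (the documents do not give the reference ranges).

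- Week 25: slightly below LLN, so notable under the SAP.
- Later visit: below 8.0 g/dL, so still notable under the SAP.
- Notable status was present at Week 25, so the later value is not newly occurring and the patient is not counted.
- Judged against the Table 15-1 cut itself, the criterion was absent at Week 25 and present later, so the patient would count.

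The same logic holds for an HbA1c already above ULN that later reaches 7.5%, and for platelets already below LLN that later fall below 75000, provided the reference limits are less extreme than those cuts. For eGFR and average glucose the gap is simpler: protocol 6.4.4.2 lists creatinine and fasting glucose, and no SAP row counts the two Table 15-1 quantities.

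**Step 3: isolated bilirubin.**

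| Isolated TBL, multiple of ULN | Protocol Appendix 1 | SAP rows that can contain it |
|---|---|---|
| >1.5 to 2 | Laboratory trigger | >1.5 |
| >2 to 3 | Liver event | >1.5 |
| >3 | Liver event | >1.5 and >3 |

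The first two bands give identical entries. The combination rows need raised ALT/AST or ALP, and Hy's law as the protocol defines it needs ALT or AST >3 x ULN, so neither picks up an isolated elevation. If the newly-occurring rule is applied row by row, a patient in the first band at Week 25 who moves to the second enters no row of the count table.

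**Step 4: what is left at the interim.** In the visible text of SAP 3.8, the notable table is the only laboratory output for Population II. By-visit summaries, liver shift tables and listings are not named there for that population. Nor does the text say whether the liver table, which also uses the word notable, is included.

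**The case against.** The strongest reply is that no analysis rule is broken. Table 15-1 is guidance, its stated use is alerting during conduct, and protocol 9.5.2 neither names it nor asks for a count table. That stands: this is a mismatch between the documents and a loss of information.

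A reader might go further and infer that the laboratory outputs cannot show clinically relevant changes. The documents do not support that. The SAP gives minimum and maximum by treatment and visit, lists all parameters for any subject with an abnormal value, and adds graded liver rows, liver shift tables and change tables. Clinically relevant deviations are to be assessed as adverse events (protocol 6.4.4 and 7.1), and liver events are classed as AESIs or SAEs (7.3), so they can also reach the adverse-event tables.

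A reader might also infer that most patients would be flagged. That does not follow. A chance of at least one out-of-range result across all analytes describes no row that the SAP specifies, and it ignores the exclusion of values already present at Week 25.

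Nor is the bilirubin >2 x ULN cut absent altogether: only the standalone row is missing, and such a patient can still fall in the >1.5 row.

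Finally, the interim centers on efficacy, and the DMC reviews unblinded safety data periodically (protocol 8.4). This lowers the stakes, but the interim also feeds program decisions, and its named laboratory output for Population II is this table.

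**Conclusion.** The point holds as a gap in the summary tables. Six of nine Table 15-1 criteria, including all five non-liver ones, have no count row. The newly-occurring rule can omit patients who worsen from mildly abnormal to beyond a Table 15-1 cut. The protocol's isolated TBL >2 x ULN liver event cannot be separated from the 1.5-2 trigger band when TBL does not exceed 3 x ULN.

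How many patients this affects cannot be stated, because the documents give neither reference ranges nor Week 25 laboratory distributions. The conclusion rests on two readings: that laboratory values follow the vital-signs rule for newly occurring, as the SAP indicates, and that the reference limits are less extreme than the Table 15-1 cuts. At the final analysis the listings and other outputs limit the harm. At the interim, for Population II, they are not named.

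**What to change.** Change the SAP text and table shells as follows.

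1. Keep the LLN/ULN summary, but title it as values outside the normal range. Replacing it outright would drop most analytes from any newly-occurring summary, and the SAP plans shift tables only for liver tests and enzymes.
2. Add newly-occurring rows for the Table 15-1 criteria, each judged against its own threshold at Week 25. State how eGFR and average glucose are derived, and whether the absolute bilirubin criterion gets its own row or is represented by the >1.5 x ULN row.
3. Add a standalone TBL >2 x ULN row to the liver table, with a note on how known Gilbert syndrome is handled.
4. Define Hy's law as in protocol Appendix 1.
5. State in SAP 3.8 that the interim notable-laboratory output includes the liver table.

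The thresholds are already in the protocol and no new data collection is needed. The cost is a few more table rows and the derivation text.

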### Liver [REDACTED] enzyme abnormalities

Newly occurring or worsening liver enzyme abnormalities will be summarized, for each population separately, using:

- Number of subjects with newly occurring notable liver [REDACTED] enzyme abnormalities will be summarized similarly to those of vital signs. Notable criteria for the table:
  - ALT or AST > 3 x ULN
  - ALT or AST > 5 x ULN
  - ALT or AST > 8 x ULN
  - TBL > 1.5 x ULN
  - TBL > 3 x ULN
  - ALP > 2 x ULN
  - ALP > 5 x ULN
  - ALT or AST > 5 x ULN & TBL > 2 x ULN
  - ALP > 5 x ULN & TBL > 2 x ULN
  - Hy's law

- Shift tables of LFTs/[REDACTED] enzymes presenting a cross-tabulation of Week 25 and worst post Week 25 values
- Change from Week 25 summary tables of LFTs/[REDACTED] enzymes by visit.

### Adverse events

Summaries will be provided for:

- Adverse events by SOC and PT

- Adverse events by severity
- Treatment emergent adverse events (Population I only)
- Post-treatment adverse events (Population II only)
- Death

█ [REDACTED]  
Adverse events of special interest (AESI)

Summary by treatment group in this study will be provided for Populations I and II separately.

All by-patient data listings will be sorted by Population, treatment group, center and patient if not indicated otherwise.

Adverse events continuing from the core study but not worsening in severity during the extension, will also be entered in the extension study database. These adverse events, will be presented in the listings but not in the tables. Adverse events continuing from the core study, but worsening in severity during the extension, will be entered as new events in the database and will be included in both tables and figures.

In addition to summary tables, safety topics of interest such as: cardiovascular events spontaneous muscle contractions; diarrhea and diarrhea-like events defined in the Safety Profiling Plan (SPP) will be listed separately.

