2.2 Secondary objectives

- To evaluate the long term safety effect of bimagrumab following treatment withdrawal as assessed by measures such as vital signs, clinical laboratory variables, electrocardiogram (ECG), and adverse events (AE)
- To evaluate the durability of effect of BYM at week 49 as measured by:
 - 6MWT
 - usual gait speed over 4 meters
 - total lean body mass (LBM) and appendicular skeletal muscle index (ASMI) measured by dual energy X-ray absorptiometry (DXA)

3 Investigational plan

[figure not shown]

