6.1.2 Other characteristics at study entry

At the core study week 25 EOT visit before a patient enters the extension study, the investigator must review the following baseline data of the core study (CBYM338E2202): Cardiovascular History eCRF, Medical History eCRF. Any cardiovascular or medical history that is still ongoing at week 25 EOT of the core study must be recorded on the Cardiovascular History eCRF or Medical History eCRF of the extension study.

Similarly, any concomitant medications ongoing at week 25 EOT of the core study must be recorded on the Prior and Concomitant Medications eCRF of the extension study.

In addition, any ongoing AEs at week 25 EOT of the core study must be recorded as AEs in the extension study eCRF.

Instructions for completing the extension study eCRF will be provided in the eCCGs.

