7.1 Adverse events

[figure not shown]
An adverse event (AE) is any untoward medical occurrence (i.e., any unfavorable and unintended sign [including abnormal laboratory findings], symptom or disease) in a subject or clinical investigation subject. Therefore, an AE may or may not be temporally or causally associated with the use of a medicinal (investigational) product.

All patients who have signed informed consent and are entered into the study will have all adverse events occurring after informed consent is signed recorded on the Adverse Event eCRF.

Pre-existing medical conditions/diseases (i.e., Medical History) are considered AEs if they worsen after providing written informed consent. Abnormal laboratory values or test results constitute AEs only if they induce clinical signs or symptoms, or are considered clinically significant, or they require therapy.

The occurrence of adverse events should be sought by non-directive questioning of the subject at each visit during the study. Adverse events also may be detected when they are volunteered by the subject during or between visits or through physical examination, laboratory test, or other assessments.

Clinically significant abnormal laboratory values or test results should be identified through a review of values outside of normal ranges/clinically notable ranges, significant changes from baseline or the previous visit, or values which are considered to be non-typical in patients with underlying disease. Investigators have the responsibility for managing the safety of individual subject and identifying adverse events. Alert ranges for liver related events are included in [Appendix 1](#).

Adverse events must be recorded on the Adverse Events eCRF under the signs, symptoms or diagnosis associated with them, and accompanied by the following information:

1. the severity grade (mild, moderate, severe)
 - mild: usually transient in nature and generally not interfering with normal activities
 - moderate: sufficiently discomforting to interfere with normal activities
 - severe: prevents normal activities
2. its relationship to the study treatment (no/yes), or investigational treatment (no/yes), or other study treatment (non-investigational) (no/yes), or both or indistinguishable,
3. its outcome, or if the event is ongoing an outcome of not recovered/not resolved should be reported.
4. whether it constitutes a serious adverse event (SAE)
5. action taken regarding study treatment

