### **Adverse events of special interest (AESI)**

The number (n) and percentage (%) of patients with adverse events of special interest will be summarized by risk level PT (levels 1-7) and treatment group. For each risk level PT, exposure-adjusted incidence rate (IR), will be calculated as the number of patients experiencing at least one AE in each category relative to the total patient years of the “at risk”\*100. The total patients years of the “at risk” is defined, as the the sum of time in years to first occurrence of a particular AE or time in years to EOS visit for subject who did not encounter a particular AE. For Population I, for each treatment group, total exposure will be calculated as the sum of exposure (days) of all patients per treatment group, divided by 365.25 (years). The calculation formula, for the number of days of drug exposure can be found in Section 3.3.1.

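### Core-study adverse events that continue past Week 25 without worsening are listed but not tabulated, so no visible AE table shows by core treatment whether they resolve off drug

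*SAP*

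**What the plan says.** The first secondary objective (Protocol 2.2) is "To evaluate the long term safety effect of bimagrumab following treatment withdrawal as assessed by measures such as vital signs, clinical laboratory variables", ECG and AEs.

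For data capture, Protocol 6.1.2 requires that "any ongoing AEs at week 25 EOT of the core study must be recorded as AEs in the extension study eCRF". Protocol 7.1 asks for each AE's outcome: "its outcome, or if the event is ongoing an outcome of not recovered/not resolved should be reported". It also asks that each AE be followed until it has gone or is considered permanent.

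For reporting, SAP 3.6.1.2 (Adverse events) divides carried-over events in two:

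- No increase in severity: "Adverse events continuing from the core study but not worsening in severity during the extension, will also be entered in the extension study database". Then: "These adverse events, will be presented in the listings but not in the tables".
- Increase in severity: such events "will be entered as new events in the database and will be included in both tables and figures".

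For Population II, AEs are summarised by start date in two intervals: Week 25 to Week 25 + 35 days, and Week 25 + 36 days onward. The AESI rate divides patients with at least one event by total time at risk. That time runs to the first occurrence, "or time in years to EOS visit for subject who did not encounter a particular AE".

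**The concern.** Population II receives no study drug in the extension. Once drug stops, a reader wants to know two things about AEs: what new events appear, and whether events that arose on drug go away. The planned tables address the first. For the second, an event that began in the core study and continues at the same grade is visible only in by-patient listings, whether it clears soon after Week 25 or is still present at Week 49. A listing does not give a proportion resolved by core treatment, so the trial would not report off-drug reversibility of AEs by arm, although it collects the data to do so.

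The AESI rate raises a related question. A patient who enters with the AESI already present is not at risk of a first occurrence, but under the carry-over rule would count as event-free with full follow-up.

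**Working it through.** **Where each kind of event is reported**

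| Status of the event | Reported in |
|---|---|
| Absent at Week 25, starts later | Tables and listings |
| Ongoing at Week 25, later worsens in severity | Tables, figures and listings |
| Ongoing at Week 25, does not worsen, resolves | Listings only |
| Ongoing at Week 25, does not worsen, persists to end of study (EOS) | Listings only |

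The last two rows are the gap: no visible table separates them.

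**Could the core-study report supply the answer?** No. SAP 3.6.1.2 (Treatment emergent adverse events) says that, for patients entering the extension, Week 25 is the last core visit. What happens to an ongoing event after that is recorded only in the extension.

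**How long is the unreported period?** The scheduled last core dose is at Week 21. An event still present at Week 49 has lasted 49 − 21 = 28 weeks beyond it, of which 49 − 25 = 24 weeks fall in the extension.

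**What is still tabulated?** SAP 3.6.1.2 gives by-visit summaries of vital signs, ECG and laboratory values. For liver tests it adds shift tables and change from Week 25. A liver abnormality already present at Week 25 therefore does appear in a table. New and worsened AEs, serious AEs, deaths and AESIs are summarised as well.

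**Effect on the AESI rate.** SAP 3.6.1.2 (Adverse events) names AESIs among its summaries and then states the carry-over rule. The AESI paragraph says nothing about an event already present at Week 25. I therefore apply the carry-over rule and assume that no carried-over AESI worsens. Let c be the number of patients with a new case, T_s the time at risk of patients without the AESI at Week 25, and T_o the time of patients who already have it.

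- Planned rate = 100 × c / (T_s + T_o)
- Rate among those truly at risk = 100 × c / T_s
- Planned ÷ at-risk rate = T_s / (T_s + T_o) = 1 − p, where p = T_o / (T_s + T_o)

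In Population II, full follow-up runs from Day 1 to Day 169 (Protocol Table 6-1). Each such patient therefore adds up to 168 / 365.25 = 0.46 patient-years. The documents give no value for p. Assumed values, for scale only:

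| p (assumed) | Planned rate as a fraction of the at-risk rate |
|---|---|
| 0.05 | 0.95 |
| 0.10 | 0.90 |
| 0.20 | 0.80 |

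The effect is always downward. It is larger in whichever arm has more ongoing events at entry.

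**Is a table useful for Population I?** About 45 patients (Protocol 3.1) are spread over four core groups, each split 1:1 (Protocol 5.2). That makes eight assigned arms, or seven regimens because both placebo arms are alike: 45 / 8 = 5.6 or 45 / 7 = 6.4 patients per arm. Those who continue bimagrumab also say nothing about reversal off drug.

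**The case against.** The best defence is that the rule is sound for the tables it governs. An incidence table should not count a core-study onset as an extension event, and the SAP itself says that on-drug events cannot be fully identified from the extension database alone. This stands, and nothing here asks for carried-over events to be added to those tables.

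It is also fair to say that the events are not hidden. They are in listings sorted by population and treatment group. Spontaneous muscle contractions and diarrhea, two of the common events named in Protocol 3.6, get separate listings, and Protocol 9.5.2 says that safety topics of interest will be analysed as well as listed. The same Protocol 3.6 describes acne and diarrhea as transient, so persistence may prove rare. One item in the SAP's list of AE summaries is blacked out, and the Safety Profiling Plan is not available. All of this limits the claim to visible tables, but none of it supplies an outcome summary by core treatment.

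A reader might infer that all carried-over AEs are kept out of every safety table. The documents do not support that: worsened events are tabulated, and the vital-sign, ECG, laboratory and liver shift tables do not depend on this rule. A reader might also infer that the safety objective cannot be answered. It does not mention AE resolution specifically, and most of its named measures are tabulated. Nor is persistence reported as absence, since the listings show it.

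On the AESI rate, the text leaves events ongoing at entry unaddressed, so the downward effect depends on applying the carry-over rule. If that rule does not apply, the AESI table departs from the rule stated just before it. Either way the SAP should say what is done.

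**Conclusion.** The point holds in a limited form. Core-study AEs ongoing at Week 25 that do not worsen are listed and not tabulated, and no visible AE table gives their resolution or persistence by core treatment. This bears on the objective of safety after withdrawal and leaves it partly, not wholly, unserved. The size is unknown, because the documents contain no count of AEs ongoing at Week 25 and no basis for guessing the share that persists.

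The AESI rate is lowered by the proportion p of at-risk time that comes from patients who already have the event. This rests on applying the carry-over rule to the AESI table. The planned new-onset tables are not in error; the SAP lacks one further summary and one definition.

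**What to change.** Keep the new-onset and worsening tables as they are, and make two changes in SAP 3.6.1.2.

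1. For Population II, by core treatment, add one table of AEs and AESIs ongoing at Week 25: patients with the event, number resolved by EOS, and number still ongoing at EOS. Because the protocol expects 30% dropout, state how a patient with no known outcome at EOS is shown. For Population I, at about six patients per arm, the listings suffice.
2. In the AESI incidence rate, exclude patients who have that AESI ongoing at Week 25 from the time at risk. For consistency, they should then not enter the numerator for that AESI; an event that worsens still appears in the AE tables.

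The data are already in the extension eCRF. The cost is SAP wording, one table and slightly longer safety output.
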